### **7.2.2 Sampling Technique**

This study will utilise opportunistic sampling techniques to engage eligible clinicians, care workers and service users in the research.

All clinician participants will be recruited from community mental health services within ELFT, and all care worker participants will be recruited from care homes identified from Care Quality Commission websites and local authority and national registers. Once eligible clinicians and care workers have consented to the study, they will screen and identify service users who meet the inclusion criteria. Clinicians and care workers will ask the service users for consent to give their contact details to a CSO or researcher. If consent is given, service users will be approached about the study by the local research team.

## 7.3 Recruitment

### 7.3.1 Sample Identification

*For Clinicians and Care Workers:*

#### Work package 1a: Piloting DIALOG+

The adapted DIALOG scale and intervention (aDIALOG+) will be piloted with 5 clinicians (any background e.g. nurse, occupational therapist, psychiatrist, social worker) from community ID teams in the East London NHS Foundation Trust (ELFT) and 5 care workers who will be recruited (via links with the community ID teams).

#### Work package 2: A feasibility study of delivering aDIALOG+ in clinical services

Clinicians will be recruited from community ID services in east London from five NHS Trusts.

#### Work package 3: A feasibility study of aDIALOG+ in care homes

We will recruit ten care homes and their care workers (approximately three to five staff in each care home) from East London, Bedfordshire and Cornwall. Care homes will be identified from Care Quality Commission websites and local authority and national registers. We will also use the ENRICH network (Enabling Research in Care homes) to identify care homes that are interested in research. We will approach the service managers at the care home and seek permission for staff to take part.

*For Service Users:*

For the clinical services, eligible service users with ID will be identified from the case load of the participating clinician through the review of medical records. They will then be approached by the participating clinician or CSO to take part in the study and an information sheet will be provided. For the care home, eligible service users with ID will be identified from service records / clinical notes by care workers, and the research team will ask staff to approach eligible service users to take part in the study. If they are interested, their details will be passed to the research team, who will contact the potential participant, provide an information sheet, and assess their eligibility and capacity to consent. Service users will receive £20 gift vouchers for each follow up/interview to reimburse them for their time.

### 7.3.2 Consent

*For Clinicians and Care Workers:*

Clinicians from community ID services in ELFT will be approached by the study research assistants or Clinical Studies Officers (CSOs) from Local Clinical Research Networks and invited to take part in the study. They will receive an information sheet and will need to provide consent to take part.

We will approach the service managers at selected care homes from East London, Bedfordshire and Cornwall and seek permission for staff to take part. We will provide care workers with an information sheet and they will need to provide consent to take part in the study.

*For Service Users:*

If the potential participant is interested in taking part, the CSO or study research assistant will contact the person and their carer to discuss the study. Accessible (easy read)

information sheets will be provided to service users with ID, and if they are unable to read, the information sheet will be read out to them by the research assistant, with support from their carer. The research assistant/ CSO will explain the study, including any potential advantages and disadvantages of taking part. They will assess capacity according to Mental Capacity Act guidelines, including whether the individual has understood the information and potential risks and benefits of taking part and that there would be no negative consequences if they chose not to take part; whether they can retain the information; weight up the information; and communicate their decision to take part. Service users will be given at least a few days so that they have time to take in the information and speak with their carer, as well as again with the clinician / care worker if they need to.

If they agree to take part, they will be asked to provide written consent using an accessible consent form, or if they cannot write, they can give verbal consent, which will be audio-recorded. A hard copy of the consent form should also be completed on their behalf by the research assistant / CSO who is taking consent, which will also specify that they have given consent verbally. For feasibility participants who do not have English as their first language, we will assess whether we can use interpreters to support the consent process and within each aDIALOG+ session with a clinician/care worker. As the number of non-English speakers taking part is likely to be small, we will not translate the information sheet into different language but can consider specific requests for translation. Research staff will receive training on how to conduct capacity assessments in people with ID, as well as awareness of unconscious bias and cultural competence. If service users consent to take part in the study the research team will inform their GP of their participation via letter.

If service users with ID initially have capacity, but lose their capacity during the study, we will withdraw the person from the study but data collected previously will be retained. We will not include any participants who lack capacity to consent. The research team will have regular contact with participating clinicians and care workers, and they will make them aware if any information becomes available during the course of the research that may be relevant to continued participation which participants need to receive. Additionally, if a service user moves out of the borough or is unexpectedly hospitalised during the study the data collected previously will be retained but the service user will be withdrawn, unless they are only hospitalised briefly (e.g. for a few weeks) and may still be able to participate.

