#### **1 BACKGROUND**

##### **What is the problem being addressed?**

Learning or intellectual disability (ID) affects 2% of the population and is characterised by limited cognitive ability and impaired adaptive functioning, arising before the age of 18 (1). People with ID experience social inequalities such as unemployment, have limited social networks and are less likely to be involved in community groups or leisure activities (2), which may impact their quality of life. They also have higher rates of physical and mental health comorbidities but experience inequities in accessing health services compared to the general population (3-5).

Behaviour that challenges (e.g. aggression/self-injury) occur in 18% of people with ID living in the community (6) and over 50% in inpatient settings (7). Reducing behaviour that challenges is important because of its detrimental impact as individuals are exposed to restrictive practices and abuse, inappropriate psychotropic medication, exclusion from day services, accommodation breakdown (8-10) and admission to psychiatric hospitals (11). The causes of behaviour that challenges in people with ID include physical and mental health conditions, and social factors contributing to a poor quality of life (QoL) such as inadequate support, leisure activities, relationships and housing (12). There is evidence that QoL may act as a mediator in the relationship between ID and behaviour that challenges (13) and psychiatric symptoms are strongly associated with behavioural problems (14-15). One plausible mechanism is that poor QoL leads to boredom and frustration, contributing to anxiety or low mood, and finally irritability and aggression. Therefore, addressing and improving QoL is a key target for interventions aiming to reduce challenging behaviour.

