## **Why this research is important and potential impact**

Individuals with ID displaying aggressive behaviour are a significant burden on health and social care services and have increased contact with services (30). As well as reducing

human suffering and distress for individuals, there could be significant cost savings if admissions are avoided and this is an urgent priority for the NHS (31). There are costs incurred from family carer distress and burden, contributing to individuals moving from family homes into residential placements; and staff burnout and poor staff retention in care homes leading to residential placements breaking down. Interventions such as PBS are time and resource intensive, difficult to access due to long waiting lists and are poorly implemented (32). Consequently, psychotropic medications are often prescribed inappropriately rather than addressing the problem but cause significant side effects (33). Rationalising their use is a national priority (31, 34).

Adapted DIALOG+ could improve the culture and delivery of care in clinical services and care homes, by providing staff with key skills that enhance person centred care during routine interactions. This could increase staff competence and resilience and improve sustainability of residential placements, leading to reduced placement breakdowns. Empowering individuals with ID to make changes that improve their QoL could reduce behavioural problems, thus reducing exposure to psychotropic medications, hospital admissions and NHS and social care costs.

This research may contribute to future clinical guidelines (e.g. NICE guidelines on challenging behaviour) and NHS and social care policies. As DIALOG+ is already being implemented in several NHS trusts, aDIALOG+ could be integrated into community ID services with relative ease.

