##### 2. Retention:

We will record the number of clinicians and service users who dropped out of the study and reasons, and the number of participants that complete the follow-up assessment.

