## 6. Completion of outcome measures:

Assessments will be conducted at baseline and post intervention (6 months) by the research assistants or CSOs and will take place face-to-face or conducted remotely (telephone or videoconference depending on preference). Outcomes will be assessed in both service users and participant carers. We will examine the proportion of participants who complete the following outcomes:

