### iii. Service use

Information about health and social care contacts and medication in the preceding six months will be collected using a modified version of the Client Services Receipt Inventory (CSRI) (51). The CSRI has been used in previous economic evaluations in people with ID and will be adapted for use in this study (52). The number and duration of contacts with primary care, professionals within community ID services (e.g. psychiatrists, nurses, social workers), secondary care (outpatient, Accident and Emergency visits and hospital admissions), day services, medication, paid and unpaid carer input and contacts with criminal justice system, will be collected. All measures will be administered with participant carers but we will also explore the feasibility of collecting information using electronic patient records.

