Statistical analysis (work package 1b): We will examine the distribution, variability and mean/median scores for each of the items. In order to assess concurrent and convergent validity, we will examine spearman's correlation between the items relating to subjective quality of life on the aDIALOG scale and the other measures. We will assess test re-test reliability by calculating the intra class correlation coefficient (ICC). Items that show poor distribution, variability and poor test re-test reliability may be removed from the scale. We will measure the internal consistency of the items relating to subjective quality of life and the treatment aspects separately using Cronbach's alpha.

Statistical analysis (WP 2 and WP 3): The feasibility outcomes will be the main focus of analysis and descriptive statistics, with associated measures of precision appropriately accounting for clustering, will be used to assess recruitment and retention, adherence, response rates in completing the outcome measures, demographic and clinical data, and cost data. We will explore changes in the scores of the outcome measures using paired t-tests or non-parametric tests where appropriate. The primary outcome measure of changes in behaviour will be measured using the Aberrant Behaviour Checklist (ABC)- irritability subscale (43). For secondary outcomes we will measure changes in behaviour (Behaviour Problems Inventory- short form) (53), quality of life (WHOQOL Disabilities module) (40), community participation (Guernsey Community Participation and Leisure Assessment – Revised) (44), psychological distress (Clinical Outcomes in Routine Evaluation, 14 item version) (42), psychiatric disorders (Moss Psychiatric Assessment Schedule - Check) (45), global improvement (Clinical Global Impression Scale) (46), health related quality of life (modified version of the EQ-5D-3L for people with ID) (48, 49) and service use (the Client Services Receipt Inventory) (51). The frequencies of adverse and serious adverse events will also be reported.

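### Withdrawing service users after a move out of borough or a non-brief unexpected admission is likely to make the 6-month data informatively missing; end of sessions and end of data collection should be separated

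*Protocol*

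**What the plan says.** Protocol section 7.3.2 (Consent) sets the rule, which applies both to a move out of the borough and to an unexpected admission: "unexpectedly hospitalised during the study the data collected previously will be retained but the service user will be withdrawn". The sentence then makes an exception: "unless they are only hospitalised briefly (e.g. for a few weeks) and may still be able to participate". The exception covers admissions only; people who move have none. The preceding rule in the same paragraph, on loss of capacity, pairs withdrawal from the study with keeping earlier data in the same way. The natural reading is therefore that data collection ends, not only the sessions.

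Other parts of the Protocol bear on this:

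- Section 1 (Background) lists "accommodation breakdown (8-10) and admission to psychiatric hospitals (11" among the harms that follow from behaviour that challenges. Section 2 (Rationale) says that "there could be significant cost savings if admissions are avoided".
- Section 5 schedules outcome assessments at baseline and 6 months only, in both WP2 and WP3.
- The service-use inventory (CSRI) looks back over six months and covers "secondary care (outpatient, Accident and Emergency visits and hospital admissions", among other items.
- On analysis: "We will explore changes in the scores of the outcome measures using paired t-tests or non-parametric tests where appropriate". The minimal important difference for the ABC Irritability subscale (ABC-I) is to be found by linking its change to the global improvement rating (CGI-I), which is made at 6 months.
- On retention: "We will record the number of clinicians and service users who dropped out of the study and reasons", together with the number who complete follow-up.

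**The concern.** The rule makes a post-baseline event the reason for not measuring the outcome, and the Protocol itself treats the event as related to that outcome. People with a long admission, or a move caused by placement breakdown, are plausibly among those whose behaviour did not improve. If they leave the dataset, the people left in the 6-month comparison are on average those who remained settled.

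Three outputs are affected. Paired change scores, and the ABC-I/CGI-I pairs used for the minimal important difference, lose these users. The CSRI loses the longer stays, because the exception keeps only the short ones. The retention rate, which is a main parameter of the study, falls partly through a study rule and not through unwillingness to continue. A planner of the later trial would read all three figures without knowing how much of each came from the rule.

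**Working it through.** **1. What a withdrawn user still contributes.** With assessments only at 0 and 6 months, withdrawal in between leaves the baseline, any app data already stored, a withdrawal form and, for an unexpected admission, a serious adverse event form. It leaves no 6-month ABC-I, CGI-I or CSRI. A paired test needs both values, so the user drops out of it.

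**2. The Protocol's own precision figure, as a yardstick.** Inputs from section 7.2.1: rate 75%, 30 service users, 12 clinicians, ICC 0.04.

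- Design effect = 1 + (30/12 − 1) × 0.04 = 1.06.
- Standard error = √(0.75 × 0.25 × 1.06 / 30) = 0.0814.
- Half width with t on 11 df = 2.201 × 0.0814 = 17.9 points, which agrees with the stated 18%. With the normal value it is 1.96 × 0.0814, or about 16 points. This figure is not in dispute.

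**3. Retention.** Suppose that each person withdrawn under the rule would otherwise have been assessed.

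- Each such withdrawal costs 1/30 = 3.3 points in WP2 and 1/40 = 2.5 points in WP3.
- Three withdrawals cost 10 points in WP2 or 7.5 in WP3. The WP2 figure compares with an 18-point half width.
- At 75% retention, WP2 expects 30 × 0.25 = 7.5 losses, so three would be 3/7.5 = 40% of them.

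**4. Mean change (assumed inputs).** Let w be the share withdrawn under the rule and D the amount, in SD of change, by which their change is worse than that of those who remain. The completers' mean is then too favourable by w × D.

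| Withdrawn of 30 | w | D = 0.5 | D = 1.0 | D = 1.5 |
|---|---|---|---|---|
| 1 | 0.033 | 0.017 | 0.033 | 0.050 |
| 2 | 0.067 | 0.033 | 0.067 | 0.100 |
| 3 | 0.100 | 0.050 | 0.100 | 0.150 |

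For comparison, with 30 × 0.75 = 22.5 completers the standard error of mean change, ignoring clustering, is 1/√22.5 = 0.21 SD.

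**5. Inpatient days (assumed inputs).** If the lost admissions last 30 to 90 days and occur in 1 to 3 of 30 users, the CSRI misses between 0.033 × 30 = 1 and 0.10 × 90 = 9 days per enrolled participant.

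The values of w, D and length of stay do not come from the documents, which give no admission rate, move rate or ABC-I variance.

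**The case against.** There is a good deal to be said on the other side.

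- *Every hospitalised user is withdrawn.* A reader might infer this if the sentence is cut short. It is not so: brief admissions may stay in. The exception does not remove the problem, since the prolonged stays are the ones lost and the criterion is discretionary.
- *The rule removes the worst outcomes.* A reader might infer this too, but the documents support only a likelihood. A move may be neutral or welcome, and an unexpected admission may be for physical illness.
- *Admissions disappear from the data.* They do not. Section 9.1 requires every serious adverse event to be logged, unexpected hospitalisation qualifies, and frequencies are reported. What is lost is the CSRI account of number and duration of contacts. A move leaves no such event record.
- *Retention is miscounted.* It is not. Reasons for dropout are recorded, so the causes can be separated, although the Protocol does not say that they will be. The effect also makes retention look worse.
- *The minimal important difference is biased in a known direction.* The documents do not show this. The analysis loses pairs, but losing people who worsened does not obviously shift the ABC-I change among those rated improved.
- *Few people are affected.* The WP2 and WP3 exclusion criteria remove people expected to move, or to be admitted, soon. That lowers the number but cannot reach events that arise later.
- *Change and cost are secondary.* This is correct: feasibility outcomes are the main focus, score changes are exploratory, and the economic aim is feasibility of data collection. Section 4.1 nevertheless lists completion and change of outcomes, cost data collection and the minimal important difference as objectives.
- *Follow-up may be impractical.* This stands in part. In WP3 the informant is the main key worker, and in WP2 a paid carer must have at least six months with the person. After a move or long stay, that informant may have lost contact and a replacement may be ineligible.

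**Conclusion.** The concern holds in a limited form. For people who move out of the borough, or whose unexpected admission is not brief, section 7.3.2 ends data collection on events that the Protocol ties to the target behaviour and to cost. Missing 6-month data are therefore likely to be informative: favourable for change and for inpatient use, unfavourable for retention.

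The size is unknown. Under the assumed ranges the effect on mean change is small to moderate (0.02 to 0.15 SD) and below its own standard error. The effect on retention could reach 10 points in WP2, and the effect on recorded inpatient days could be substantial because the long stays are the ones removed. These are illustrations that rest on the assumed shares and differences above, and on withdrawn users doing worse on average. They do not show that any estimate is biased by a given amount. The rule does not defeat the feasibility aims, but it creates avoidable missing data.

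**What to change.** In section 7.3.2, define two separate states: no longer receiving aDIALOG+ sessions, and withdrawn from data collection. Then state the following:

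- Unless consent is withdrawn or capacity is lost, the 6-month measures are still sought for anyone who moves or is admitted. Section 5 already allows assessments that "will take place face-to-face or conducted remotely (telephone or videoconference depending on preference".
- Informant measures come from the original informant where that person still knows the service user. Any change of informant is flagged, so that the pair can be set aside in a sensitivity analysis.
- Service use is taken from records where available; the Protocol already plans to explore this.
- Those assessed count as completing follow-up, and loss due to the rule or the event is reported separately from voluntary dropout.
- The brief-admission exception is worded so that sites apply it in the same way.

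The cost is a few sentences in the Protocol, a line in the information sheet and a few extra remote assessments. Recovery will be incomplete where the informant has lost contact. The loss-of-capacity rule is unchanged, and nothing here bears on whether sessions should continue after a move or an admission.

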## **8 END OF STUDY**

The end of the research study will occur on the date that the last 6-month follow-up questionnaire and qualitative focus group/interview have been completed, which will mark the end of the data collection activity.

## **9 ETHICAL AND REGULATORY CONSIDERATIONS**

### **9.1 Assessment and Management of Risk**

We do not anticipate any unintended consequences/ adverse events. Safety concerns will be discussed with the study steering committee and the ethics committee will be informed if necessary. This may lead to termination of the study or the study may be paused until the issue is investigated. As this is a feasibility study, there will not be a data monitoring committee.

It will be explained to all participants that participation is voluntary, that they can withdraw at any time without providing an explanation, and that their care will not be affected if they do not participate in the study. Baseline and follow-up assessments will be conducted face-to-

face where possible but we will accommodate remote assessments if participants express a preference. Assessments may be carried out in clinic settings or in service user's homes based on their preference. We have kept the number of measures to a reasonable number in order to reduce burden on service users and carers, and where possible we have used short versions of measures. We will provide £20 gift vouchers to service users and carers to thank them for their time for completing qualitative interviews and after the baseline assessment and prior to the follow-up assessments.

To maintain participant and researcher safety, we will ensure that risk assessments are conducted prior to meeting the service user, especially if they are going to be seen in their home. This will involve reviewing existing risk assessments, and if one is not available, researchers will seek information from the referrer. If there is a potential risk of physical aggression to researchers, each case will be discussed with their line manager / supervisor and arrangements will be made to ensure risks can be mitigated (e.g. carrying a personal alarm, ensuring service user is seen with their carers). Lone working policies will be followed for home visits.

If service users become distressed during their aDIALOG+ sessions or during end of study interviews, sessions will be stopped or service users will be offered a break and given the option of continuing or rescheduling the session. We will discuss concerns with the service user's clinical team.

If there are safeguarding issues (e.g. participants disclose abuse or there is a risk of harm to themselves or others), we will follow the service's safeguarding policy (e.g. to raise safeguarding alert). In this situation, we will seek permission from the individual to raise a safeguarding alert but if they do not provide permission, we will explain that confidentiality will need to be broken as there is a professional obligation to report such issues. Research assistants will discuss these issues with the local PI and study CI and all incidents will be recorded.

